### 9.1 Primary Endpoint

The primary endpoint is successful revascularization after the final pass of NIMBUS, as determined by an Independent Core Lab, where the successful revascularization is defined as achieving an mTICI score of 2b or greater.

### 9.2 Secondary Endpoints

Secondary endpoints are listed below; further details about these endpoints are provided above in Section 3.2.2 of this protocol. There are no prospectively stated hypotheses associated with these secondary endpoints.

- 1) Successful Procedural Revascularization (final mTICI  $\geq$  2b).
- 2) Excellent Procedural Revascularization (final mTICI  $\geq$  2c).
- 3) First Pass Revascularization using NIMBUS (mTICI  $\geq$  2b).
- 4) Occurrence of Embolization to a New Territory (ENT).
- 5) Symptomatic Intracerebral Hemorrhage (sICH) at 24 hours specified according to the Heidelberg Bleeding Classification (HBC).
- 6) 90 Day All-Cause Mortality.
- 7) Modified Rankin Scale (mRS) of  $\leq$  2 at 90 days.

### 9.3 Ancillary Endpoints

Other analyses are listed below; further detail about these analyses is provided above in Section 3.3 of this protocol. There are no prospectively stated hypotheses associated with these analyses.

1) Clot Analysis

- Histopathologic analysis of clots collected

2) Hospitalization Analysis

Medical Resource Utilization and Health Economics related data including:

- Hospitalization length of stay for index procedure and unscheduled re-hospitalizations.
- Healthcare resource utilization for index procedure, post-procedure and re-hospitalizations for unscheduled events.

### 9.4 Levels of Significance

No formal tests of hypothesis are planned. Unless otherwise stated, all confidence intervals will be two-sided 95%.

### 9.5 Analysis Sets

The following analysis sets are defined in the study:

**Modified Intent-to-Treat (mITT) Analysis Set:**

The mITT Analysis Set consists of all subjects who are enrolled into the study, and who have attempted at least one pass with the NIMBUS device (which includes deployment and retrieval with the NIMBUS device).

**mRS Analysis Set:**

In order to define a population more comparable to prior published literature reporting mRS outcomes at 90 days, the mRS Analysis Set has been defined. The mRS Analysis Set consists of all mITT subjects who meet all of the following criteria at baseline:

- MRI criterion: volume of diffusion restriction visually assessed  $\leq 50$  mL.
  - OR
  - CT criterion: ASPECTS 6 to 10 on baseline CT.
    - OR
    - CTA-source images, or, volume of significantly lowered CBV  $\leq 50$  mL.
- NIHSS  $\geq 8$  and  $< 30$
- Subjects treated within 6 hours of onset of stroke symptoms (start of treatment defined as groin puncture)

### 9.6 Sample Size Justification

There is no hypothesis testing for this post-market study, approximately 50 treated subjects are deemed sufficient to evaluate the performance of NIMBUS.

Approximately 50 subjects will be consecutively enrolled using commercially available Mechanical Thrombectomy devices during the preceding one or two passes. With an enrolled sample size of up to 50

and an attrition rate of no more than 10%, the precision (margin of error) for the primary endpoint is anticipated to be around 10.1% based on 2-sided 95% confidence intervals, where the primary endpoint rate is estimated to be 86%.

*Margin of error*  $\approx 1.96 \times SE$

$$= 1.96 \times \sqrt{\frac{p(1-p)}{n}} = 1.96 \times \sqrt{\frac{0.86 \times (1-0.86)}{45}} = 10.1\%$$

where  $SE$  denotes the standard error and  $p$  denotes the proportion of subjects who achieve the primary endpoint.

## 9.7 Analyses to be Conducted

### 9.7.1 General Conventions

Descriptive summary statistics will be presented for all endpoints. The number and percentage of subjects will be summarized for categorical variables. Descriptive statistics for continuous variables will include the number of subjects, mean, standard deviation, median, minimum and maximum.

### 9.7.2 Disposition of Study Subjects

The number and percentage of subjects in the mITT Analysis Set, together with a summary of subjects who were excluded (i.e. ineligible consented subjects), completed or discontinued the study with associated reasons, will be summarized for all consented subjects.

Enrollment by site will be summarized for all enrolled subjects.

### 9.7.3 Demographic and Baseline Characteristics

All demographic characteristics, procedural, and immediate post-operative data will be summarized using the mITT Analysis Set.

### 9.7.4 Primary and Secondary Endpoint Analyses

There are no prospectively stated hypotheses associated with primary or secondary endpoints.

All analyses will be summarized using the mITT Analysis Set unless otherwise defined.

#### 9.7.4.1 Primary Endpoint Analysis

##### 1. Successful Revascularization (mTICI $\geq 2b$ ) with NIMBUS as determined by an Independent Core Lab.

The endpoint is defined as the number and percentage of subjects who have achieved mTICI score of 2b or greater after the final pass of NIMBUS. Two-sided exact 95% confidence intervals will be conducted around the percentage.

Subjects with missing data on mTICI will be excluded from the analysis.

The mTICI score will be based on the assessment from the Independent Core Laboratory.

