## 2 OBJECTIVES AND PURPOSE

The objective of this study is to assess the efficacy of NIMBUS in a real-world setting in patients where the first one or two passes with another Mechanical Thrombectomy therapy have not achieved mTICI 2b or better.

The rate of effectiveness achieved will be considered as we design further studies. The study will also report on clot characteristics and clinical outcomes.

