#### 4.1 Inclusion Criteria

Prior to entry in this study, patients must meet **ALL** of the following criteria:

1. Age  $\geq$  18.
2. The subject or the subject's legally authorized representative has signed and dated an Informed Consent Form.
3. Patient has had one or two passes of another mechanical thrombectomy device without achieving mTICI 2b or better and continues to have angiographic confirmation of a Large Vessel Occlusion (LVO) in the same vessel.
4. mRS 0-1 prior to this stroke.
5. NIMBUS is used on the second or third overall pass to attempt revascularization.

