#### **5.3 Independent Core Laboratory for Image Evaluation**

All imaging collected will be SOC, no additional imaging will be requested for this study. Imaging should include full A-P lateral images for the start and the end of each procedural pass. An independent radiographic core laboratory shall be utilized to provide an unbiased and standardized assessment of all collected imaging. All subject protected health information will be removed before an image is uploaded and evaluated. The core lab assessor will be blinded to subjects' previous medical history. Each angiogram will be read independently by experienced Imaging Core Lab neuro-interventionalists.

The objective of the Imaging Core Lab will be to:

- Review all angiograms obtained
- Provide an unbiased assessment of the rate of revascularization defined by mTICI scores based on angiographic imaging from the study sites
- Evaluate CT/MRI examinations to detect and assess hemorrhages.

This study will be collecting the following imaging data to be assessed by Imaging Core Lab:

- Baseline - CT/ MR imaging
  - Infarct volume
  - Clot location
  - Clot length
  - Clot radiodensity on CT / Susceptibility Vessel Sign (SVS) on MRI
- Procedural Angiography
  - mTICI score for every pass
  - Clot location for every pass (proximal face of clot)
  - Emboli to new territories
- Post Procedure - CT/ MR imaging
  - Intracranial Hemorrhage

Hemorrhages will be classified according to the following categories [36]:

- HI 1 – Scattered small petechiae, no mass effect
- HI 2 – Confluent petechiae, no mass effect
- PH1 – Hematoma within infarcted tissue, occupying <30%, no substantive mass effect
- PH2 – Hematoma occupying 30% or more of the infarcted tissue, with obvious mass effect
- RIH – Parenchymal hematoma remote from infarcted brain tissue
- IVH – Intraventricular Hemorrhage
- SAH – Subarachnoid Hemorrhage
- SDH – Sub Dural Hemorrhage

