### **6.1 Screening**

Subjects presenting with AIS to the enrolling medical treatment facility will be evaluated and treated by the physician according to the institutional practice prior to enrolment in the study. A subject can be consented to participate in this study from the point of imaging confirming a large vessel occlusion up to 7 days post-procedure. Subjects will be screened against the study inclusion/exclusion criteria to determine their initial eligibility. The final eligibility criterion is the requirement for a second pass of a mechanical thrombectomy device during the index procedure, therefore, the screening log should be completed post procedurally for all AIS patients in whom a second mechanical thrombectomy pass was completed. All subjects screened will be documented on the Screening/Enrolment log, including the reason for non-participation for subjects who do not enroll.

All assessments and imaging performed for this study are part of SOC for stroke treatment. Informed consent is mandatory and must be obtained before any data is captured in the eCRF.

During the eligibility screening, the investigator will perform an initial evaluation of potential study subjects for study eligibility according to inclusion / exclusion criteria. For subjects who meet the eligibility criteria and agree to participate, informed consent will be obtained. The investigator, or designee, will explain the research study to the subject and/or the legally authorized representative and answer any questions that may arise. The possible risks and possible benefits of participation will be discussed. The subject and/or the legally authorized representative will be asked to read, review and sign the EC approved informed consent form. The informed consent process is detailed further in Section 10.3.

**A subject is considered enrolled in this study after the physician confirms the subject meets all eligibility criteria, and the subject is consented.**

All subjects *who provide written informed consent* will be entered into eCRF regardless of whether or not they participate in the study.

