## 6.3 Procedure Assessments

Immediately prior to introducing a guide catheter, the physician will perform an angiogram of the affected intracranial artery. The angiogram will be done using standard techniques (subtracted complete runs from arterial to venous phase initially and at end of procedure). The purpose of the pre-procedure angiogram is to confirm:

- the location of the occlusion;
- that the subject remains suitable for treatment with mechanical thrombectomy;
- that the subject remains a candidate for the study per the eligibility criteria.

In the event that the subject is excluded as a result of the angiogram, the subject will be considered a screen-failure and will not require any study follow-up.

Subjects will have challenging occlusions, with mTICI  $\leq$  2a post one, or two passes, of another Mechanical Thrombectomy device. Any commercially available Mechanical thrombectomy device (i.e. either aspiration or Stent-retriever other than NIMBUS) may be used during the first and up to two vessel clearance attempts. The physician may use his own discretion on whether to introduce the NIMBUS after one failed vessel clearance attempt, or after two. The NIMBUS must be used no later than the overall third procedural pass for the patient to be eligible. Up to 50 subjects will be treated with the NIMBUS.

Once the decision has been made to use NIMBUS, it is used for up to three passes. After the third pass with the NIMBUS, if the physician would like to utilize another device/technique for treatment, they may. Angiographic imaging will be collected per every pass for subsequent review by an independent Imaging Core Lab. Clot will also be collected per every pass for analysis in an independent Central Lab.

Endovascular treatment with NIMBUS, and the other stent-retrievers, is performed per hospital standard technique and in accordance with the applicable devices' IFU.

The following data will be captured during the procedure, and recorded on the eCRF:

- Name of the treating physician.
- Type of sedation used.
- Vessel location of the occlusion being treated per pass.
- mTICI scores per pass (Pre-device deployment and post-device retrieval).
- Names and sizes of stent-retrievers used per pass.
- Lot number of NIMBUS used, as applicable.
- Ancillary devices used (e.g., balloon guides, microcatheters) per pass.
- Details of the technique used per pass.
- Relevant time points during the procedure (e.g. arterial puncture time).

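### Does the primary rate need a companion figure for subjects the core lab itself graded 2a or lower before NIMBUS?

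*Protocol*

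**What the plan says.** The objective (Protocol 2) is efficacy in real-world use "in patients where the first one or two passes with another Mechanical Thrombectomy therapy have not achieved mTICI 2b or better". It does not say whose reading decides that the earlier passes failed.

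Inclusion criterion 3 (Protocol 4.1) requires that failure and adds that the patient "continues to have angiographic confirmation of a Large Vessel Occlusion (LVO) in the same vessel". Protocol 6.1 gives the confirmation to the treating side: "A subject is considered enrolled in this study after the physician confirms the subject meets all eligibility criteria". Protocol 6.3 leaves the timing of the device to the operator: "The physician may use his own discretion on whether to introduce the NIMBUS after one failed vessel clearance attempt, or after two".

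The core lab reads the angiograms afterwards. Protocol 5.3 lists among its outputs "mTICI score for every pass", and also says "All imaging collected will be SOC, no additional imaging will be requested for this study".

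The primary endpoint (Protocol 9.7.4.1) is "the number and percentage of subjects who have achieved mTICI score of 2b or greater after the final pass of NIMBUS", analysed in the mITT set with an exact two-sided 95% interval. Membership of mITT needs enrolment and one NIMBUS pass, with no condition on the core-lab grade before NIMBUS. SAP 7.5.1 keeps this definition. When the core-lab grade after the final NIMBUS pass is missing, it substitutes the core lab's end-of-procedure grade under stated conditions.

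Protocol 9.7.4.2 item 3 stratifies the core-lab results by the grade before the first NIMBUS pass, against both the post-first-pass and the post-final-pass grade. SAP 7.10 carries this out as two shift tables and leaves end-of-procedure scores out of the post-final one. SAP 7.9 allows further subgroups, without intervals.

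**The concern.** Entry rests on one assessor and success on another. If the operator reads 2a before NIMBUS and the core lab later reads 2b on the same run, the subject enters the study as a failure of earlier treatment and can leave it as a NIMBUS success with no change in the core-lab grade. Nothing in the primary analysis separates such subjects.

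The rate is to be considered when further studies are designed (Protocol 2). If many subjects were of this kind, the headline figure would partly describe what the first device achieved. Two further points made the gap look larger. No pooled rate or interval is written for subjects the core lab put at 2a or lower. And the post-final shift table may omit grades that the primary endpoint substitutes, so its rows might not add up to the primary counts.

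**Working it through.** **The plan's own figure.** Protocol 9.6 works from a rate "where the primary endpoint rate is estimated to be 86" per cent, with 50 enrolled and 10% attrition, so n = 50 × 0.90 = 45.

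1.96 × sqrt(0.86 × 0.14 / 45) = 0.1014, or 10.1 points. This reproduces.

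**Effect on the primary rate.** Let Q be the share of analysed subjects already at 2b or better by core lab before NIMBUS, ret the share of these still at 2b or better after the final NIMBUS pass, and r the success rate in the rest.

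- Full rate = Q × ret + (1 − Q) × r
- Full rate − r = Q × (ret − r)

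The documents give no value for Q or ret. Only the planned 86% can stand in for r; 60% is an assumed lower value.

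| r | ret | Q = 5% | Q = 10% | Q = 20% |
|---|---|---|---|---|
| 86% | 100% | +0.7 | +1.4 | +2.8 |
| 86% | 86% | 0 | 0 | 0 |
| 86% | 80% | −0.3 | −0.6 | −1.2 |
| 60% | 100% | +2.0 | +4.0 | +8.0 |
| 60% | 80% | +1.0 | +2.0 | +4.0 |

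The sign is not fixed. It is upward only if subjects already at 2b or better keep that grade more often than the others reach it.

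**In counts.** Assume 45 analysed, 5 of them already at 2b or better, and 34/40 = 85.0% in the rest (exact 95% interval 70.2 to 94.3).

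- All 5 keep the grade: 39/45 = 86.7% (73.2 to 94.9), +1.7 points
- One worsens: 38/45 = 84.4% (70.5 to 93.5), −0.6 points
- Two worsen: 37/45 = 82.2% (67.9 to 92.0), −2.8 points

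With 24/40 = 60.0% in the rest (43.3 to 75.1), the same three cases give 29/45 = 64.4%, 28/45 = 62.2% and 27/45 = 60.0%, that is +4.4, +2.2 and 0 points.

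**How common it would have to be.** At full retention the shift equals the 10.1-point margin when Q = 0.101 / (1 − r).

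- r = 86%: 0.101 / 0.14 = 72% of subjects
- r = 60%: 0.101 / 0.40 = 25% of subjects, or 0.25 × 45 ≈ 11

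A group of that size would be plain in the planned tables.

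**What the planned tables yield.** On the scale in Protocol Table 2, grades of 2a or lower are rows 0, 1 and 2a. In the table from before the first NIMBUS pass to after the final one, the sum of those rows is the denominator of the restricted rate, and their cells at 2b50 or above are the numerator. An exact interval follows from those two counts. The rows at 2b50 and above show how many subjects started there, and their cells show how many kept the grade or lost it.

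**The substitution rule.** SAP 7.5.1 substitutes only if the final NIMBUS pass was the last procedural pass, nothing further was done (no later intervention, no intra-arterial lytic), and an end-of-procedure core-lab grade exists. In such a subject the end-of-procedure grade describes the vessel after the final NIMBUS pass. SAP 7.10's exclusion can be read as dropping that value, or simply as saying that the end-of-procedure result is not what the table tabulates. The documents do not size this group.

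**The case for a change.** The strongest case for a change is that the 10.1-point margin describes sampling error and says nothing about who is counted, so a shift inside it can still be systematic. The rate in subjects whom the endpoint's own assessor graded 2a or lower matches the stated population most directly. SAP 7.9 would not supply it: no intervals are given for subgroups, and results appear only with at least 10 subjects in every level, which is 10/45 = 22% for the already-2b level. If the problem is uncommon, that subgroup would not be shown. One more SAP line would cost little, since the grades are already collected.

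The reading of the text stands: the primary rate has no core-lab condition before NIMBUS, and the pooled rate is not written down. The possible mismatch of counts also stands as a small ambiguity. SAP 7.7 adds to it by saying no other imputation is planned although SAP 7.5.1 and 7.5.2 contain such rules; there the specific rule plainly governs.

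The case for acting does not follow. The shift tables have no minimum-size rule, so rare cases appear in them. The device is introduced on the operator's judgement, so the full mITT rate describes the patients met in use. The restricted rate has weaknesses of its own: it depends on the core lab's grade of the run before NIMBUS, drops subjects who had 2b and lost it, and cannot place subjects without a gradable run before NIMBUS, which can occur because only standard-of-care imaging is collected.

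**Conclusion.** No change is needed. The primary analysis is a legitimate description of the treated population, and the planned core-lab tables let a reader separate subjects already at 2b or better before NIMBUS. What is absent is one pooled line that an analyst can form by adding rows, give or take any subject with a substituted or missing grade.

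The size rests on assumed values. For Q from 5% to 20%, the shift is at most +2.8 points at the planned 86% and +8 points at an assumed 60%; it falls to zero or reverses as retention drops. All these values lie inside the plan's 10.1-point margin. The requirement for a continuing large-vessel occlusion in the same vessel should keep Q low, though the documents give no figure. With no hypothesis test (Protocol 9.4) and intervals meant only to convey precision (SAP 4), the missing line does not alter what the study can conclude. Only a large Q, about a quarter of subjects or more at r = 60%, would bring the shift up to the plan's margin, and the planned tables would show it.

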#### **9.7.4.2 Secondary Endpoint Analyses**

##### **1. Successful Procedural Revascularization (final mTICI $\geq$ 2b)**

This endpoint is defined as the number and percentage of subjects who have achieved the mTICI score of 2b or greater following the final pass of the procedure.

The mTICI score will be based on the assessment from the Independent Core Laboratory from the end of the procedure.

##### **2. Excellent Procedural Revascularization (final mTICI $\geq$ 2c)**

This endpoint is defined as the number and percentage of subjects who have achieved the mTICI score of 2c or greater following the final pass of the procedure.

The mTICI score will be based on the assessment from the Independent Core Laboratory from the end of the procedure.

##### **3. First Pass Revascularization using NIMBUS (mTICI $\geq$ 2b)**

This endpoint is defined as the number and percentage of subjects who have achieved the mTICI score of 2b or greater following the first NIMBUS pass.

In addition, the number of subjects who achieved each mTICI category will be reported. The analysis will be stratified using the mTICI score pre the first NIMBUS pass compared to the mTICI score post the final pass of NIMBUS. The analysis will also be performed stratified using the mTICI score pre the first NIMBUS pass compared to the mTICI score post the first pass of NIMBUS.

All mTICI scores will be based on the assessment from the Independent Core Laboratory.

##### **4. Occurrence of Embolization to a New Territory (ENT)**

The occurrence of embolization to previously unaffected territory will be recorded, as evaluated from procedural imaging by the independent Imaging Core Lab. This endpoint is defined as the number and percentage of subjects with ENT following the final pass of NIMBUS. The two-sided exact 95% confidence interval will be conducted around the percentage.

##### **5. Symptomatic Intracerebral Hemorrhage (sICH) at 24 hours specified according to the Heidelberg Bleeding Classification (HBC)**

sICH is defined as a new intracranial hemorrhage as detected by brain imaging, measured 24 hours after intervention. The number and percentage of subjects with sICH at 24 hours post-procedure as assessed by HBC will be summarized. The two-sided 95% confidence interval will be conducted around the percentage.

##### **6. 90 Day All-Cause Mortality**

The incidence of all mortality regardless of cause at 90 days post-procedure will be summarized. The two-sided exact 95% confidence interval will be conducted around the percentage.

##### **7. Modified Rankin Scale (mRS) of $\leq$ 2 at 90 days post-procedure**

The mRS is a scale commonly used to measure the degree of disability or dependence in the daily activities in subjects following stroke or other neurologic events and is conducted by a qualified independent evaluator. It is a scale with seven categories ranging from no symptoms (score 0) to severe disability and death (score 6). The mRS scores will be collected at baseline, and 90 days post-

procedure, and if assessed, at discharge and unscheduled visits. The 90 day mRS must be performed by a qualified independent evaluator who is not part of the interventional treating team.

This endpoint is defined as the number and percentage of subjects who reached mRS score of  $\leq 2$  at 90 days post-procedure and will be analyzed in the mRS Analysis Set population. The two-sided exact 95% confidence interval will be conducted around the percentage.

